#### 8.1.2 Unscheduled visits

Unscheduled visit measurements of laboratory data, vital signs, and ECG will be used for computation of baseline and worst values and/or grades. Re-windowing for unscheduled visits will not be performed.

#### 8.1.3 Duplicated visits

Depending on the statistical analysis method, single values may be required for each analysis window. For example, change from baseline by visit usually requires a single value per visit. Unless otherwise noted throughout the rest of this document, when a single value is needed, the following rule(s) will be used:

- If more than 1 assessment occurs during the same nominal visit, select the record closest to the nominal day for that visit.
- If there are 2 assessments that are equidistant from the nominal day, the data of the assessment after the scheduled study day will be used.
- The last measurement will be used if multiple measurements are taken on the same day.

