3 STUDY OBJECTIVES AND ENDPOINTS

Table 3 Study Objectives and Endpoints

Primary	
Objectives	Endpoints

Phase 1:
 
• To characterize the safety and tolerability of loncastuximab tesirine in combination with ibrutinib, and to identify the MTD/recommended dose and schedule for future studies 
Phase 2:
 
• To evaluate the efficacy of loncastuximab tesirine given at every cycle in combination with ibrutinib in patients with relapsed or refractory DLBCL	
Phase 1:
 
• Frequency and severity of adverse events (AEs) and serious adverse events (SAEs)• Incidence of dose-limiting toxicities (DLTs) (dose escalation only)• Frequency of dose interruptions and dose reductions• Changes from baseline of safety laboratory values, vital signs, Eastern Cooperative Oncology Group (ECOG) performance status, and 12-lead electrocardiograms (ECGs) 
Phase 2:
 
• CRR according to the 2014 Lugano classification (Cheson et al., 2014) as determined by independent review committee (IRC) in all DLBCL patients given loncastuximab tesirine at every cycle in combination with ibrutinib; CRR defined as the proportion of patients with a best overall response (BOR) of complete response (CR)

Table continued on next page.

Secondary	
Objectives	Endpoints

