8.3.7 ECG

Three consecutive (also called triplicate) 12-lead ECGs will be performed at defined time points throughout the study as per the SoE ([Table 1](#) and [Table 2](#)). Refer to [Table 8](#), [Table 9](#), and [Table 10](#) for the detailed schedule of ECGs.

The ECGs should be performed after the patient is resting for at least 5 minutes.

At time points coinciding with blood sample collection including PK, and ECGs should be taken prior to blood collection, and where applicable, before vital sign measurements (refer to [Figure 2](#)).

If a patient experiences Torsade de Pointes, additional concomitant PK samples (i.e., unscheduled) should be collected.

Table 8 Schedule for Triplicate ECG Collection: Phase 1

Cycle	Day	ECG Time point (window)
Screening		Any time within 28 days prior to C1D1
C1	D1	Pre-dose (preferably within 2 h prior to start of infusion) EOI (within 10 min prior to EOI) Post-dose* 4 h (± 15 min)
	D8	Post-dose* 168 h (± 48 h; but within 30 min prior to PK sample)
	D15	Post-dose* 336 h (± 48 h; but within 30 min prior to PK sample)
C2	D1	Pre-dose (within 30 min prior to PK sample) EOI (within 10 min prior to EOI) Post-dose* 4 h (± 15 min)
	D8	Post-dose* 168 h (± 48 h; but within 30 min prior to PK sample)
	D15	Post-dose* 336 h (± 48 h; but within 30 min prior to PK sample)
C3	D1	Any time (but within 30 min prior to PK sample)
EOT		Any time (but within 30 min prior to PK sample)
Unscheduled		Any time

Abbreviations: ECG, electrocardiogram; EOI, end of infusion; EOT, end of treatment; PK, pharmacokinetics.

*Post-dose time point is counted from start of infusion.

Table 9 Schedule for Triplicate ECG Collection: Phase 2 for Cohort Where Loncastuximab Tesirine Is Given Intermittently in Combination with Ibrutinib

Cycle	Day	ECG Time point (window)
Screening		Any time within 28 days prior to C1D1
C1	D1	Pre-dose (preferably within 2 h prior to start of infusion) EOI (within 10 min prior to EOI) Post-dose* 4 h (\pm 15 min)
	D8	Post-dose* 168 h (\pm 48 h; but within 30 min prior to PK sample)
	D15	Post-dose* 336 h (\pm 48 h; but within 30 min prior to PK sample)
C2	D1	Pre-dose (within 30 min prior to PK sample) EOI (within 10 min prior to EOI) Post-dose* 4 h (\pm 15 min)
	D8	Post-dose* 168 h (\pm 48 h; but within 30 min prior to PK sample)
	D15	Post-dose* 336 h (\pm 48 h; but within 30 min prior to PK sample)
C3	D1	Any time (but within 30 min prior to PK sample)
C5	D1	Pre-dose (preferably within 2 h prior to start of infusion)

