C6	D1	Pre-dose (preferably within 2 h prior to start of infusion) EOI (within 10 min prior to EOI)
C9	D1	Pre-dose (preferably within 2 h prior to start of infusion)
C10	D1	Pre-dose (preferably within 2 h prior to start of infusion) EOI (within 10 min prior to EOI)
EOT		Any time (but within 30 min prior to PK sample)
Unscheduled		Any time

Abbreviations: ECG, electrocardiogram; EOI, end of infusion; EOT, end of treatment; PK, pharmacokinetics.

*Post-dose time point is counted from start of infusion.

Table 10 Schedule for Triplicate ECG Collection: Phase 2 for Cohort Where Loncastuximab Tesirine Is Given at Every Cycle in Combination with Ibrutinib

Cycle	Day	ECG Time point (window)
Screening		Any time within 28 days prior to C1D1
C1	D1	Pre-dose (preferably within 2 h prior to start of infusion) EOI (within 10 min prior to EOI) Post-dose* 4 h (\pm 15 min)
	D8	Post-dose* 168 h (\pm 48 h; but within 30 min prior to PK sample)
	D15	Post-dose* 336 h (\pm 48 h; but within 30 min prior to PK sample)
C2	D1	Pre-dose (within 30 min prior to PK sample) EOI (within 10 min prior to EOI) Post-dose* 4 h (\pm 15 min)
	D8	Post-dose* 168 h (\pm 48 h; but within 30 min prior to PK sample)
	D15	Post-dose* 336 h (\pm 48 h; but within 30 min prior to PK sample)
C3 and beyond	D1	Pre-dose (preferably within 2 h prior to start of infusion)
EOT		Any time (but within 30 min prior to PK sample)
Unscheduled		Any time

The ECGs will be submitted for a central review. Submission instructions for the central review will be provided in a separate manual. Assessments will include determination of heart rate and rhythm and the PR, QRS, QT, QTcF, and QTcB intervals.

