9.8.3 Additional Safety Assessments

The results of scheduled assessments of vital signs, physical examinations, ECOG performance status, and 12-lead ECGs will be summarized. All data will be reported according to the nominal visit date for which it was recorded (i.e., no visit windows will be applied). Unscheduled data will be included in “worst case” summaries, which will capture a worst case across all scheduled and

unscheduled visits after the first dose of study drug. All data will be listed. Further details will be provided in the SAP.

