## 5 Statistical methods

All analyses will use SAS® version 9.4 or higher.

Unless otherwise stated, tables, listings, and figures will be broken down by cohort (non-GCB DLBCL, GCB DLBCL, all DLBCL and MCL). Additional tables include Phase 1 tables by dose level for safety, demographic and dosing, Phase 1 tables by dose level for dose escalation patients only, and tables of 60 µg/kg and 75 µg/kg loncastuximab tesirine in both Phase 1 and 2 by cohort. Tables and figures are based on the defined analysis population.

Categorical data will be presented using counts and percentages, with the number of patients in the analysis population as the denominator for percentages. Percentages will be rounded to 1 decimal place and not be displayed for zero counts.

Continuous data will be summarized using the number of observations (n), mean, standard deviation (std), median, minimum, and maximum. Minima and maxima will be rounded to the precision of the original value, and means, medians, and 95% confidence intervals (CIs) if presented will be rounded to 1 decimal place greater than the precision of the original value. The std will be rounded to 2 decimal places greater than the precision of the original value, up to a maximum of 3 decimal places.

CI will be two-sided and use  $\alpha=0.05$  (i.e., 95% CIs), unless otherwise specified. For exact estimates, the CI will be calculated using the Clopper-Pearson exact method. For Kaplan-Meier estimates, the CI will be calculated using the Greenwood's formula with (complementary) log-log transformation.

Kaplan-Meier plots will be provided along with Kaplan-Meier estimates.

The Baseline value is defined as the last non-missing value or measurement taken prior to the first dose of study drug.

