### **5.10.3 Electrocardiogram**

Electrocardiogram (ECG) data will be summarized for the actual value and the change from baseline value at each scheduled assessment. Shift tables will summarize the shift from baseline to EOT and worst post baseline visit in ECG interpretation (categorized as normal; abnormal, not clinically significant; and abnormal, clinically significant).

Corrected QT interval by Fredericia (QTcF) will be summarized by categories as follows:

- QTcF interval > 450 ms
- QTcF interval > 480 ms
- QTcF interval > 500 ms
- QTcF interval increases from baseline > 30 ms
- QTcF interval increases from baseline > 60 ms

Listings of ECG data will be provided.

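### SAP sections 5 and 8.1.3 have no exception for triplicate ECGs: applied literally they use one tracing rather than the triplicate mean, and only the last time point on C1D1 and C2D1

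*SAP*

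**What the plan says.** **Collection.** Protocol 8.3.7: "Three consecutive (also called triplicate) 12-lead ECGs will be performed at defined time points throughout the study". Tables 8, 9 and 10 all schedule three ECG time points on C1D1 and on C2D1: pre-dose, end of infusion (EOI) and 4 h. Table 9 (Phase 2, intermittent dosing) also has pre-dose and EOI time points on C6D1 and C10D1.

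**Central review.** Protocol 8.3.7: "The ECGs will be submitted for a central review". It lists the intervals to be determined, QTcF among them, and refers to a separate manual for submission. It does not say whether the review returns a value per tracing or a mean per triplicate.

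**Baseline.** SAP section 5: "The Baseline value is defined as the last non-missing value or measurement taken prior to the first dose of study drug".

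**Default for multiple values.** SAP 8.1.3: "Unless otherwise noted throughout the rest of this document, when a single value is needed, the following rule(s) will be used". Its own example of such a need is change from baseline by visit. For several values on one day: "The last measurement will be used if multiple measurements are taken on the same day".

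**ECG analysis.** SAP 5.10.3: "Electrocardiogram (ECG) data will be summarized for the actual value and the change from baseline value at each scheduled assessment". It adds shift tables and QTcF categories, and mentions neither replicates nor averaging. Protocol 9.8.3 has no averaging rule either and leaves further detail to the SAP. SAP 8.1.2 lets unscheduled ECGs count towards baseline and worst values but is silent on replicates.

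**The concern.** A triplicate is taken so that its mean can damp tracing-to-tracing variation. Every rule in the SAP that would reduce several ECG readings to one selects a reading; none averages. Followed as written, the rules pay for three tracings and use one in the change-from-baseline summary. A noisy single-tracing baseline also enters every later change value for that patient.

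The same-day wording creates a second problem. It refers to the day, not the time point. On C1D1 and C2D1 a by-visit value chosen this way would come from the 4 h ECG alone, and the planned pre-dose and EOI values would drop out of the by-visit summary for those days.

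The stake is modest. ECG change is one item in a bundled Phase 1 primary safety endpoint (Protocol section 3: "Changes from baseline of safety laboratory values, vital signs, Eastern Cooperative Oncology Group (ECOG) performance status, and 12-lead electrocardiograms (ECGs"), and it is summarised descriptively.

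**Working it through.** The documents give no QTcF SD, precision target or ECG-based sample size, so there is no plan figure to reproduce. The check has two parts.

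**1. What the rules do if applied literally**

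- C1D1 and C2D1 each have 3 time points × 3 tracings = 9 tracings.
- SAP 8.1.3 first picks the record closest to the nominal day. All nine share the day, so the same-day rule decides and keeps the last: one tracing, from the 4 h time point.
- On days with one ECG time point (for example C1D8 or C3D1) it keeps one tracing of three.
- Under SAP section 5, baseline is the last single tracing before the first dose.

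**2. Effect on the variance of QTcF change**

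Let s_c be the SD of true change between the two occasions, s_r the SD between replicates within a triplicate, and m the number of tracings averaged at each occasion. With independent replicate errors:

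Var(change) = s_c² + 2·s_r²/m

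The replicate part is 2·s_r² for m = 1 and 2·s_r²/3 for m = 3, a ratio of 3 whatever s_r is. At s_r = 8 ms it is 128 against 42.7 ms².

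The ratio of total variances depends on both SDs, which are **assumptions**: s_r 5–10 ms and s_c 8–21 ms. The upper end of s_c corresponds to a between-occasion SD of 15 ms, since √2 × 15 = 21.2. The last two columns give the chance of an apparent increase above 30 ms at one time point when the drug has no effect (normal distribution, one-sided tail).

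| s_c | s_r | Var, m = 1 | Var, m = 3 | Ratio | SD, m = 1 | SD, m = 3 | P(>30), m = 1 | P(>30), m = 3 |
|---|---|---|---|---|---|---|---|---|
| 21.2 | 5 | 450 + 50 = 500 | 450 + 16.7 = 466.7 | 1.07 | 22.36 | 21.60 | 9.0% | 8.2% |
| 8 | 5 | 64 + 50 = 114 | 64 + 16.7 = 80.7 | 1.41 | 10.68 | 8.98 | 0.25% | 0.04% |
| 10 | 8 | 100 + 128 = 228 | 100 + 42.7 = 142.7 | 1.60 | 15.10 | 11.94 | 2.35% | 0.60% |
| 21.2 | 10 | 450 + 200 = 650 | 450 + 66.7 = 516.7 | 1.26 | 25.50 | 22.73 | 12.0% | 9.3% |
| 8 | 10 | 64 + 200 = 264 | 64 + 66.7 = 130.7 | 2.02 | 16.25 | 11.43 | 3.24% | 0.43% |

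Over the assumed range the variance ratio runs from about 1.07 to 2.0. Below that range, at s_r = 3 ms, it is only 1.17 for s_c = 8 and 1.08 for s_c = 12. The direction is certain whenever replicates differ at all; the size is not.

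**The case against.** **Central review may already settle it.** If one mean per triplicate is delivered for each time point, there is nothing left to choose between within a time point and the same-day rule never meets a triplicate. This stands, and the point is conditional on it. The documents do not say which form is delivered.

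**SAP 8.1.3 was probably not written for replicates.** It is headed as dealing with duplicated visits, its other two rules concern distance from the nominal day, and the protocol tables treat a triplicate as one ECG time point. The SAP 5.10.3 reference to each scheduled assessment could also be read as keeping pre-dose, EOI and 4 h apart. That the literal result would discard planned time points suggests it was not intended. This is fair as to intent. But 8.1.3 is stated as the default, nothing in 5.10.3 overrides it in terms, and if it does not apply the SAP has no rule for three readings. Likewise, the section 5 baseline wording does not exclude a triplicate mean, but it does not call for one.

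**A stronger reading: a fixed share of the tracings is wasted.** From Table 8 a reader might count 13 time points and 39 tracings and infer that 13 are used and 26 thrown away. The documents do not support that count. It needs a per-time-point version of a rule written per day; on the literal wording there are 9 visit-days, plus a separate pre-dose baseline, so about 10 readings. Moreover, 8.1.3 operates only where a single value is needed. Worst-case summaries and listings may use every tracing.

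**The noise figures are assumed.** True. In addition, the SAP does not say that the QTcF categories are tabulated per time point, so the exceedance percentages may match no planned table. They are illustrations only.

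**The consequence is small, and the study has been discontinued.** Also true, and reflected in the grading. The SAP still plans these ECG tables.

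**Conclusion.** The point holds as a minor, conditional one. Applied as written, SAP sections 5 and 8.1.3 would use one tracing instead of the triplicate mean and, on C1D1 and C2D1, only the last time point of the day, unless central review returns one mean per triplicate for each time point.

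The certain part of the size is that the replicate component of the variance of QTcF change is three times what triplicate means would give, assuming independent replicate errors. The total-variance ratio of about 1.07 to 2.0 is illustrative and rests on the assumed SDs; at the low end the loss hardly matters.

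A reader might go further and infer that the reported mean QTcF change would be biased, or that a Phase 1 primary endpoint is compromised. Neither follows. Using one replicate adds noise, and with it chance crossings of the change thresholds, but does not shift the mean change. The ECG summary is descriptive, and no dose decision, response analysis, sample size or power figure depends on it.

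**What to change.** Add to SAP 5.10.3, as a stated exception to 8.1.3 and to the section 5 baseline definition:

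*For ECG, the value at each nominal time point (pre-dose, EOI and 4 h kept separate) is the mean of the available replicates, or the central-review triplicate mean if that is what is delivered; baseline is the mean of the replicates at the last scheduled or unscheduled pre-dose ECG time point; change from baseline, worst post-baseline value and QTcF categories use these means.*

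This covers both possible forms of central-review output, keeps same-day time points apart, and fits with SAP 8.1.2 on unscheduled ECGs. The sponsor should also confirm which form the central review delivers.

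Cost: a free improvement. It takes one SAP sentence and minor programming on data already collected.

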8.3 Safety Assessments

Safety will be assessed based on the procedures in the subsection below. The AE/SAE collection and reporting are described in [Section 8.2](#).

Unless otherwise specified, all safety assessments on dosing days will be done prior to administration of study drug(s).

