8.3.4 Vital Signs

Vital signs include the measurements of arterial BP (systolic and diastolic), heart rate, respiratory rate, and body temperature and should be performed according to the institutional standards. Vital signs should be measured before and after each loncastuximab tesirine infusion.

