### **5.10.4 Vital Signs**

Vital sign data, including height and weight, will be summarized for the actual value and the change from baseline value at each scheduled assessment.

Listings of vital sign data, including height and weight, will be provided.

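### Unless separate time points are programmed, the SAP's last-of-day rule puts post-infusion vital signs into the by-visit change-from-baseline tables on infusion days only

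*SAP*

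**What the plan says.** - **Collection.** Protocol 8.3 makes pre-dose the default time for safety assessments on dosing days unless something else is specified. Protocol 8.3.4 does specify something else: "Vital signs should be measured before and after each loncastuximab tesirine infusion". Each infusion day should therefore yield at least two readings.
- **Schedule.** Protocol Tables 1 and 2 give vital signs a single mark per visit. The ECG row of the same tables names pre-dose, end-of-infusion and 4-hour points for Day 1 of C1 and C2.
- **Analysis.** SAP 5.10.4 states: "Vital sign data, including height and weight, will be summarized for the actual value and the change from baseline value at each scheduled assessment". It does not say which reading counts on an infusion day.
- **Selection rule.** SAP 8.1.3 applies, unless noted otherwise, when a single value is needed. Its own example is that "change from baseline by visit usually requires a single value per visit". The first step is: "If more than 1 assessment occurs during the same nominal visit, select the record closest to the nominal day for that visit". The second breaks ties between days in favour of the later day. The third is: "The last measurement will be used if multiple measurements are taken on the same day".
- **Baseline.** SAP Section 5 takes the last non-missing value before the first dose of study drug.
- **Endpoint status.** Change from baseline in vital signs belongs to the Phase 1 primary safety endpoints and the Phase 2 secondary endpoints (Protocol Table 3).

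**The concern.** A change-from-baseline table is useful only if the later value is the same kind of measurement as the baseline value. Here the baseline is taken before any infusion. If the last-of-day rule applies to vital signs, the value kept on an infusion day is the one taken after the infusion. At C1D1 the tabulated change would then be a same-day difference across the infusion, presented as a change on treatment.

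Infusions are given at some cycles and not others, so the kind of reading would alternate along the visit axis. A real drift in blood pressure or heart rate could not be separated from a switch in reading type. From C2 on, the dosing-day reading comparable with baseline would drop out of the by-visit table, although it was collected. The acute infusion effect, which is of interest in itself, would not be reported as such either.

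**Working it through.** The plan states no figure to reproduce. The check applies the SAP 8.1.3 rules to the visit calendar.

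**1. Calendar.** SAP 5.8.1 sets 21-day cycles for C1 and C2 and 28-day cycles afterwards. Starting at day 1, adding 21 twice and then 28 repeatedly gives Day 1 visits on days 1, 22, 43, 71, 99, 127, 155, 183, 211, 239, 267, 295, 323 and 351. These match SAP Table 1 for C1 to C14. That is 14 Day 1 visits. Adding Days 8 and 15 of C1 and C2 gives 14 + 4 = 18 scheduled on-treatment visits with vital signs.

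**2. Which reading is kept on an infusion day.**
- Closest to the nominal day: both readings fall on the same day, so they tie.
- Later day preferred: neither is on a later day, so they still tie.
- Last reading of the day: the post-infusion reading is kept.

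Protocol 9.8.3 reports data by nominal visit without windows, so windowing does not separate the two readings. No text exempts vital signs.

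**3. Count of affected visits through C14.**

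| Group | Infusion visits (Day 1) | Of 14 Day 1 visits | Of 18 on-treatment visits |
|---|---|---|---|
| Phase 2 intermittent | C1, C2, C5, C6, C9, C10 | 6 (6/14 = 43%) | 6 (6/18 = 33%) |
| Phase 1, not re-treated | C1, C2 | 2 | 2 |
| Phase 1, re-treated | C1, C2, C5, C6 | 4 | 4 |

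The every-cycle cohort is left out because SAP Section 4 says it will not be enrolled.

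**4. What an infusion shift would do.** Let D be the mean post-minus-pre difference on an infusion day, and suppose there is no true drift. The documents give no value for D, so the check used an assumed range of -10 to +10 units. For Phase 2 intermittent, the change from baseline under the last-of-day rule is:

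| Visits | Change from baseline |
|---|---|
| C1D1, C2D1 | D |
| C1 and C2, Days 8 and 15 | 0 |
| C3, C4 | 0 |
| C5, C6 | D |
| C7, C8 | 0 |
| C9, C10 | D |
| C11 to C14 | 0 |

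With D = 5 the series moves between 5 and 0; with D = -10, between -10 and 0; with D = 0 nothing shows. Along the Day 1 visits the value moves at C2 to C3, C4 to C5, C6 to C7, C8 to C9 and C10 to C11: 5 of the 13 steps. The other 8, such as C3 to C4 or C5 to C6, are unaffected. With the pre-infusion reading the change is 0 at all 18 visits for any D.

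**5. Mixing within a visit.** In Phase 1 only patients with partial response or stable disease at Week 14 may receive C5 and C6 infusions. If a share f of patients at those visits is re-treated, the visit mean moves by f × D. For example, f = 0.5 and D = 5 (both assumed) give 0.5 × 5 = 2.5. The shift therefore depends on who is re-treated. Protocol 6.5.1 also lets ibrutinib continue when loncastuximab tesirine is delayed or stopped, so a Phase 2 visit can contain both kinds of reading too.

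**The case against.** The strongest reply is that SAP 8.1.3 need not apply. Its heading concerns duplicated visits, and two readings that the protocol plans are not duplicates. A scheduled assessment could mean each planned time point. SAP 5.10.3 uses matching wording for ECG, which plainly has several time points on Day 1 of C1 and C2. The SAP is also to be read with the case report form, which is not available here and may record the two readings separately. Alternatively, the single schedule mark could be the pre-dose reading under the Protocol 8.3 default, with the post-infusion reading as an extra.

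This stands to the extent that the outcome is conditional: with separate time points programmed, the problem does not arise. It does not remove the gap. For ECG the time points are named in the schedules and in Protocol Tables 8 to 10; for vital signs they are named in neither the schedules nor the SAP. The SAP cites by-visit change from baseline as its example of when one value is needed. A programmer following the text alone would keep the post-infusion reading.

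A second reply is that little is lost. All vital-sign data are listed, Protocol 9.8.3 plans worst-case summaries, infusion-related reactions have their own line in the adverse event overview, and no test or decision rule uses these tables. That is correct, and it limits the weight of the point.

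A third reply concerns premedication. Protocol 6.7.1 starts dexamethasone the day before the infusion where possible, and otherwise at least 2 hours before it on the day. Both readings, and the C1D1 baseline, can therefore follow dexamethasone. It does not distinguish post-infusion from pre-infusion readings, and choosing the pre-infusion reading may not remove its effect.

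**Conclusion.** Wrong as written, but limited to descriptive safety tables. If no separate time points are programmed, 6 of 14 Day 1 visits in intermittent Phase 2 and 2 or 4 of 14 in Phase 1 set a post-infusion value against a pre-infusion baseline. Complete response rate, the other efficacy endpoints and the adverse event tables are untouched.

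The conclusion assumes that both readings are taken as Protocol 8.3.4 requires, that they are stored under one nominal visit, and that SAP 8.1.3 is applied as worded.

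A reader might infer more than the documents support:
- **That post-infusion values will certainly be tabulated.** This depends on how the time points are programmed.
- **That there is a distortion of a known size in mmHg.** The documents give no infusion effect on vital signs; D above is purely illustrative and could be zero.
- **That every visit-to-visit step is distorted.** Only transitions between infusion and non-infusion visits are.
- **That non-infusion values are resting values.** Protocol 8.3.4 refers to institutional standards; the 5-minute rest is specified for ECG in Protocol 8.3.7.

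**What to change.** In SAP 5.10.4, override 8.1.3 for vital signs:
- On infusion days, the by-visit value and the change from baseline use the pre-infusion reading.
- The post-infusion reading is tabulated separately as the within-day change, post minus pre, for each infusion.
- All readings remain available for worst-value summaries.

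This makes the by-visit series comparable with baseline as far as the infusion is concerned, and shows the acute change in its own table. It does not necessarily remove any premedication effect, and a footnote should say so.

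The cost is a short addition to the SAP and one extra table, using readings the protocol already requires. The programmer must be able to tell the two readings apart, by time-point label or clock time; this should be confirmed against the case report form. No change to the protocol or to patient care is needed.
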